One plus one equals two – Will that do?

A randomized controlled trial to evaluate collegial midwifery practice to prevent perineal trauma

Project plan

2020-02-20

Ethical approval no 2018/476

Purpose and aims

The purpose of this study is to evaluate a clinical practice to reduce severe perineal trauma. This clinical practice involves collegial midwifery assistance during the second stage of labor, where an additional midwife is present during the active phase of the second stage of labor and the birth of the baby. The midwife responsible for the birth is the primary carer of the woman and the other midwife observes the birth or assists the primary midwife if asked to.

Specific aims:

Does the clinical practice with a second midwife present during the second stage and the birth of the baby

- reduce severe perineal trauma (grade III-IV)?
- reduce vaginal tears?
- reduce perineal trauma grade II?
- reduce pelvic floor-related symptoms one year after the birth?
- How do midwives divide work assignments and responsibility between them during the second stage of labor?
- How do women experience having one or two midwives attending the birth of the baby?
- How do women experience midwifery care methods used during the second stage of labor to prevent perineal trauma?

Background

Most women sustain some form of perineal trauma when giving birth vaginally (1). Perineal injuries are classified as grade I-IV (2). A first-degree tear only includes perineal skin or mucosa, whereas a second-degree tear includes muscles in the perineal body. A tear involving a part or the whole of the anal sphincter muscle complex is graded III-IV (2). Data from the Swedish National Birth Register show that 4% of first-time mothers suffered a tear affecting the anal sphincter (3). National registers in Sweden only collect data on severe perineal trauma affecting the anal sphincter but in a recent regional Swedish study 78% of the primiparous women experienced second-degree tears (4). The consequences of second-degree tears and severe perineal trauma are pain (5), dyspareunia (6), and an increased risk of symptomatic pelvic organ prolapse later in life (7). A severe consequence of perineal trauma is anal incontinence, mainly caused by tears affecting the anal sphincter muscle (8, 9). However, second-degree tears may also lead to anal incontinence (8). This may be related to a lack of support from the perineal body due to poor repair. Furthermore, perineal

trauma is known to be misclassified, with consequent under-reporting of injuries affecting the anal sphincter complex (10).

Risk factors for severe perineal trauma (grade III-IV) are giving birth vaginally for the first time, having an assisted vaginal birth, giving birth vaginally after a previous caesarean section, or giving birth to a baby that weighs more than 4000g, and the risk increases with age (1, 11-13). Some of the midwifery care methods used to prevent perineal injuries have been evaluated in clinical trials but there are still gaps in our knowledge (14). Even if scientific evidence is lacking for most of the preventive strategies used by midwives except for warm compresses held at the perineum (14), midwives believe that a slow and controlled birth is a key factor in prevention. Several studies indicate that a combination of strategies can be effective in preventing perineal trauma (4, 15-17). Giving birth is a profound experience for the woman and her partner and an experience that has significance for the woman all her life (18). The second stage is considered to be the most stressful part of the labor for the woman and her unborn baby, and consequently also for the midwife (19). Despite this, there is still a lack of knowledge about how women experience the second stage and the methods midwives use to facilitate birth and prevent perineal trauma (14). Traditionally midwives have asked colleagues for a second opinion or to assist in complicated situations, or in obstetric emergencies. Recently a new clinical practice has been introduced in approximately 50% of the maternity wards in Sweden to reduce severe perineal trauma (20). This procedure involves two midwives attending the woman during the second stage of labor. The midwife responsible for the birth calls for the second midwife when the active phase of the second stage has started and the presenting part of the baby is visible. The second midwife observes the birth and can assist the midwife responsible for the birth if needed. An unpublished survey from one maternity ward in Sweden showed that most of the midwives appreciated this way of working but were uncertain as to whether it actually reduced the prevalence of severe perineal trauma (20). Furthermore, this clinical practice might have negative side-effects or unintended consequences. The maternity wards that practise this method have not increased the number of midwives. It could be argued that there is a risk that other women in labor will be left unattended for longer periods when two midwives assist at births. How midwives share the responsibility and communicate are factors that needs to be evaluated scientifically.

Project design

This is a parallel multicentre randomized controlled trial. Women expecting their first child will be randomized to either having one midwife assisting the active phase of the second stage of labor and the birth of the baby (standard care) or to having two midwives present.

That means that if the woman is randomized to the intervention, the midwife responsible for the birth is assisting the woman as usual but asks a second midwife to be present in the birthing room ready to help her if necessary (intervention). The study is designed according to CONSORT statements (21).

The hypothesis in this study is that the collegial presence of another midwife during the second stage of labor will reduce perineal trauma grade III-IV (primary outcome).

Data from the National Birth Register show that 4.1% of first-time mothers suffered severe perineal trauma in Sweden 2017. The prevalence of severe perineal trauma varies between different regions in Sweden (3). To be able to detect a 50% reduction in severe perineal trauma grade III-IV from 4.1% to 2.0% with 80% power and a 95% level of significance, 1052 women in each group will be needed. The 50% reduction is based on regional figures after a change in practice and is therefore clinically significant. Allowing for a possible drop-out rate of 20% and another drop-out of 20% for possible cases of obstetric emergencies where another midwife will be needed regardless of randomization, this will result in 1473 women in each group and 2946 women in total.

The primary outcome is the prevalence of severe perineal tears grade III-IV.

Secondary outcomes are the prevalence of second-degree tears, vaginal tears, women's experiences of two midwives attending the birth and midwives' experiences of the intervention. Additional secondary outcomes regarding the woman are: the prevalence of episiotomy, first-degree tears, intact perineum (no tear), labial and periurethral tears, postpartum bleeding >500 ml, birth position, instrumental delivery, urinary incontinence, anal incontinence, symptoms of pelvic organ prolapse and sexual function after one year, and self-reported mental health one month and one year after birth. For the one-year follow-up the following validated questionnaires will be used: PFIQ7, PFDI-20, and FSFI and EPDS (22-24). Secondary outcomes regarding the newborn child are: Apgar scores at 1, 5 and 10 minutes, umbilical cord blood gases, and breastfeeding within two hours after birth.

Inclusion criteria: Swedish speaking women expecting their first child or with a prior caesarean section opting for a vaginal birth, with a singleton live foetus in cephalic presentation from gestational week 37+0.

Participating clinics: The maternity ward at Karolinska University Hospital Huddinge and Solna, and the maternity wards at SUS Malmö and Lund. With four participating clinics the time for patient recruitment will be shortened and this will also increase the generalizability of the results.

Randomization process: It will not be possible to blind either women or midwives in this study. The participants will be randomly allocated (1:1) to the intervention group (collegial presence of another midwife during the second stage) or to the standard care group (one midwife is responsible for the care during the second stage). Randomization will take place at the start of the second stage. To allow for equal distribution between the groups, block randomization in blocks of ten will be used. The midwife in charge will be responsible for the randomization process. Sealed and opaque envelopes will be used and will be prepared with a unique code consisting of a first code letter identifying each study site, a second code letter identifying which group it belonged to (intervention or control) followed by a consecutive number.

Data collection: After the birth the tear will be diagnosed together with a midwife or an obstetrician who has not been involved in the birth. Tears will be sutured according to the guidelines at each participating study site. The midwife responsible for the birth will complete a questionnaire which will contain questions regarding the woman; labor and birth variables, methods of preventing perineal trauma, questions regarding the newborn, diagnosis of the tear and how the tear was sutured. If a second midwife has been present during the second stage (intervention) the responsible midwife (midwife no 1) will also complete questions on the assistance she got from the second midwife and how this assistance was experienced. Data will also be retrieved from the participating women's records by using the local database of each study site (Obstetrix). When the intervention has taken place the second midwife will also complete a questionnaire. This questionnaire will contain questions on what assistance she gave the midwife responsible for the woman (if any) and how she experienced being present during the second stage of labor. The questionnaires completed by the midwives will be coded with the same code as the participating woman received when she was allocated to the intervention or standard care.

The questionnaire regarding women's experiences of the intervention or standard care and the methods used to prevent perineal trauma will be sent by email one month after the birth. The questions in the questionnaire are study specific, containing questions regarding the experience of the second stage of labour, preventive methods used, initiation of breastfeeding, perineal pain, pain medication used, and resumption of sexual intercourse. In addition the Edinburgh postnatal depression scale (EPDS) will be used to assess mental health (23). The follow-up with validated questionnaires regarding pelvic floor symptoms will be sent to the women one year after birth. For the one year follow-up, the questionnaires used are Pelvic floor impact questionnaire (PFIQ7), Pelvic floor distress inventory (PFDI-20), the Female Sexual Function Index (FSFI) and Edinburgh postnatal depression scale (EPDS)

(22, 23, 25). If the woman does not complete the questionnaire in two weeks, she will be reminded, and the questionnaire will be sent by mail.

Analysis

Descriptive statistics will be used to present the data. The means, SD, median, quartiles, and 95% CI will be calculated when appropriate as will frequency tables, stratified by the two arms. The primary statistical analysis is intention to treat but a per protocol analysis will also be performed. For comparison between the two groups, t-tests will be used for continuous variables and Chi-square tests for dichotomous variables. A possible preventive effect of having two midwives attending the second stage of labour and birth of the baby will be calculated as a relative risk of severe perineal trauma (tear grade III-IV) with 95% CI. We will adjust for study site using logistic regression. If baseline variables are not balanced by randomisation we will adjust for those using multivariate logistic regression. Response analyses regarding primary outcome will be undertaken at each study centre. Secondary outcomes will be compared using t-tests for continuous variables and Chi-square tests for dichotomous variables. The Mann-Whitney U-test will be used for outcomes based on scores. The project has access to a statistician from Clinical Studies Sweden, Forum South.

Adverse events

As approximately 50% of the maternity wards in Sweden already have implemented the clinical practice with two midwives without reporting any adverse side-effects, such as increased rates of severe perineal trauma or an increase in Apgar scores <4 at five minutes, we will not perform routine interim analyses throughout the data collection. Analyses will be performed if the maternity wards notice a negative trend in outcomes related to the mother (severe perineal trauma, postpartum haemorrhage >1000 ml) or the baby (Apgar scores and neonatal resuscitation).

Clinical significance

The number of women seeking care for pelvic floor problems related to childbirth is increasing. Improving the health and well-being for women giving birth is important on a personal level but also for society. There is an ongoing debate in the Swedish media and among women regarding severe perineal trauma. Childbirth organizations are upset that care providers are not able to prevent injuries and find it extraordinary that gaps in our knowledge still exist in this field of research. Many women are afraid of giving birth vaginally because they fear an extensive tear and the consequences such a tear might have on their

life. Some women are so fearful that they request a caesarean section. Hence, it is imperative to fill this gap in knowledge and implement and implement evidence based care. Furthermore, many interventions used in labor and birth have been introduced without any evaluation and analyses as to whether they have any unintended consequences. The results from this study will show whether this clinical practice, which approximately 50% of all maternity wards in Sweden already have adopted is preventive or not, or if it has any negative side effects. If the presence of a second midwife can be demonstrated to be preventive, the practice can be implemented in all the maternity wards in Sweden. Otherwise health care resources could be used more effectively. The results from this study will also generate knowledge about women's experiences of the midwifery care methods to prevent perineal trauma. This knowledge is currently lacking and is important as care should be both effective and of value to women.

Ethical approval 2018/476

The study has ethical approval from the Ethics committee in Lund no 2018/476 and is planned in accordance with Swedish law for research concerning humans (SFS 2003:460) and the Declaration of Helsinki regarding research involving human subjects. Research during labor and birth needs careful planning since giving birth is a profound life-experience for the woman and her partner and the woman is in a vulnerable position. At the same time, it is important to evaluate preventive methods used in clinical practice. As the intervention is already in use it has been considered possible and ethical to evaluate in a clinical trial. The study has received financial support from FORTE and SUS Funds.

References

3. The Swedish Pregnancy Register - Annual Report 2018. <https://www.medscinet.com/GR/default.aspx>: The Swedish Pregnancy Register; 2019. Contract No.: .

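### The allowance for two 20% drop-outs multiplies by 1.4 instead of dividing by the fraction retained; if both losses leave the analysis in both arms, power is about 73–76%, not 80%

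*Protocol*

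**What the plan says.** The sample-size paragraph in the Project design section of the protocol assumes a rate of severe perineal trauma (grade III–IV) of 4.1% under standard care and 2.0% with a second midwife. It states that "with 80% power and a 95% level of significance, 1052 women in each group will be needed".

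It then enlarges that number: "Allowing for a possible drop-out rate of 20% and another drop-out of 20% for possible cases of obstetric emergencies", the second group being births at which another midwife is needed whatever the allocation. The result is "this will result in 1473 women in each group and 2946 women in total". No formula is shown for this step.

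The Analysis section says: "The primary statistical analysis is intention to treat but a per protocol analysis will also be performed". Neither section says whether the emergency cases are left out of the primary analysis.

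**The concern.** To have a required number left after a loss, one divides that number by the fraction expected to remain. Adding the loss percentages to the required number gives too few, and the gap widens as the loss grows. The planned losses here are large, so the gap could matter.

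The number at issue supports the primary outcome, which is uncommon. The protocol's Clinical significance section says the result will guide whether the practice is adopted in all Swedish maternity wards or the resources are used elsewhere. A null result will be read against the stated 80% power, so that figure should be one the design delivers.

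**Working it through.** **Inputs** (Project design section unless noted)

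- Rates: p₁ = 0.041 and p₂ = 0.020, so the difference is 0.021 and the mean rate p̄ is 0.0305.
- Power 80%; significance level 5%. Sidedness is not stated and is inferred below.
- Allocation 1:1 (Randomization process).
- Two drop-outs of 20% each; 1473 per group after inflation.

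**Step 1: the plan's 1052**

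Two-sided test, pooled variance under the null, no continuity correction:

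n = [1.96·√(2·p̄(1−p̄)) + 0.8416·√(p₁(1−p₁) + p₂(1−p₂))]² / (p₁−p₂)²

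= [1.96·√(2·0.0305·0.9695) + 0.8416·√(0.041·0.959 + 0.020·0.980)]² / 0.021²

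= [0.4766 + 0.2043]² / 0.000441 = 1051.4, rounded up to **1052**.

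This matches. A one-sided test gives 829 and a continuity correction gives 1145, so neither was used.

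**Step 2: the plan's 1473**

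| Operation | Result per group |
|---|---|
| 1052 × (1 + 0.20 + 0.20) | 1472.8 → **1473** |
| 1052 × 1.2 × 1.2 | 1515 |
| 1052 / 0.80 (one loss only) | 1315 |
| 1052 / (0.80 × 0.80) | 1643.75 → 1644 |
| 1052 / 0.60 | 1753.3 → 1754 |

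Of these, only multiplication by 1.4 gives 1473. The loss that 1473 can absorb is 1 − 1052/1473 = 28.6%. The stated losses are 1 − 0.80 × 0.80 = 36% if sequential, or 40% if additive.

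**Step 3: what remains of 1473, and the power**

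Power = Φ{[(p₁−p₂)·√n − 0.4766] / 0.2427}, where 0.2427 = √(0.041·0.959 + 0.020·0.980).

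| Women leaving the analysis, both arms | Remaining per group | Power |
|---|---|---|
| Both losses, additive | 1473 × 0.60 = 883.8 → 884 | 72.9% |
| Both losses, sequential | 1473 × 0.64 = 942.7 → 943 | 75.6% |
| Target | 1052 | 80.0% |
| First 20% only | 1473 × 0.80 = 1178.4 → 1178 | 84.3% |
| None | 1473 | 91.3% |

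For example, at 884: (0.021 × 29.73 − 0.4766) / 0.2427 = 0.609, and Φ(0.609) = 0.729.

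Against the target of 1052, the shortfall is 109 (sequential) or 168 (additive) women per group. The exact binomial power of the uncorrected chi-square test is 76.6% at 943 and 74.0% at 884, so the shortfall is not produced by the normal approximation.

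**Step 4: emergency cases kept in the analysis**

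Under intention to treat, controls who receive a second midwife in an emergency remain in the control group and may narrow the contrast. The protocol gives no figure for this, so the shares and effects below are assumptions chosen to show the range. The intervention rate is held at 2.0%.

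| Assumed dilution | Control rate | Power, 1178 per group | Power, 1473 per group |
|---|---|---|---|
| None | 4.1% | 84.3% | 91.3% |
| 10% of controls get half the effect | 4.1 − 0.10 × 1.05 = 3.995% | 81.1% | 88.8% |
| 20% of controls get half the effect | 4.1 − 0.20 × 1.05 = 3.89% | 77.5% | 85.9% |
| 20% of controls have the 2.0% rate | 0.8 × 4.1 + 0.2 × 2.0 = 3.68% | 69.0% | 78.4% |

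**The case against.** The strongest reply is that 73–76% is not the power of the analysis the protocol calls primary. Women who need a second midwife in an emergency have been randomised and have an outcome, so intention to treat keeps them. Excluding both groups is closer to the per protocol analysis.

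Even the first 20% need not be lost for the primary outcome. Randomisation takes place at the start of the second stage, and the tear is diagnosed after the birth, recorded by the midwife and backed by hospital records. The follow-up most exposed to non-response is the later questionnaires, which serve secondary outcomes. With all 1473 per group analysed, power is 91.3% at the full effect. Of the three dilution scenarios, only the most extreme then falls below 80%, at 78.4%. The dilution inputs are not the protocol's and cannot show that the trial is underpowered.

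Much of this stands as a limit on the claim. The 73–76% must not be read as the power of the intention-to-treat analysis, and that power may be above or below 80%.

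It does not rescue the sample-size sentence. That paragraph labels both groups drop-out and enlarges both arms for both. If emergency cases stay in the analysis, they are not drop-outs and the allowance serves some other purpose that is not stated. If they leave, the arithmetic is wrong. The 91.3% also sets aside the first 20% loss, which the paragraph itself plans for.

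**Conclusion.** The concern holds. The base figure of 1052 is right for the stated rates; the inflation to 1473 is not. On the paragraph's own terms, 943 or 884 women per group remain instead of 1052. Power is then 75.6% or 72.9%, and the chance of missing the planned effect is about 24–27% instead of 20%.

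This rests on three conditions: both losses are removed from the analysis, they fall equally on both arms, and the test is two-sided at 5% (inferred because it reproduces 1052). The power of the intention-to-treat analysis is a separate figure that the protocol does not give. It depends on how many women lack a primary outcome and how far emergency help narrows the contrast.

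This should be corrected. It does not by itself show that the trial is too small for its primary analysis.

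**What to change.** Rewrite the inflation sentence in the Project design section: replace the 1.4 multiplier with division by the fraction retained, and say which loss applies to which analysis. Either of two forms would do.

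**(a) Keep 2946 and state the power it gives.** Suggested text:

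> With 1473 women per group, if both drop-outs are excluded from both groups, 943 (sequential losses) or 884 (additive losses) per group remain, giving about 76% or 73% power. In the intention-to-treat analysis with only the first 20% lost, 1178 per group remain, giving about 84% power at the full effect, and less if emergency help from a second midwife dilutes the contrast.

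If the investigators expect the primary outcome for nearly all randomised women, they could add the figure for 1473 per group: about 91% at the full effect, with the same caution about dilution.

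**(b) State the size that matches the claim.** With both groups excluded, 80% power corresponds to 1644 per group (3288 in total, 342 more than 2946) for sequential losses, or 1754 per group (3508 in total, 562 more) for additive losses. These totals apply only to an analysis without both groups and are not in themselves a reason to enrol more women.

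Option (a) costs one corrected passage and changes nothing in recruitment, randomisation or analysis. Its only drawback is a less favourable stated power for the analysis that excludes both groups.

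### Intact perineum is defined only as the absence of a tear and episiotomy is listed apart from second-degree tears, so on a literal reading a cut without a tear counts as no perineal injury in two secondary outcomes

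*Protocol*

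**What the plan says.** Four places in the protocol bear on this.

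- **Purpose and aims.** One specific aim asks whether the second midwife will "reduce perineal trauma grade II". The word there is trauma, not tear.
- **Background.** Injuries are graded I to IV, and "a second-degree tear includes muscles in the perineal body". Episiotomy is not placed in any grade.
- **Project design.** "Secondary outcomes are the prevalence of second-degree tears, vaginal tears" and women's and midwives' experiences. A later sentence adds "the prevalence of episiotomy, first-degree tears, intact perineum (no tear), labial and periurethral tears". The bracket after intact perineum is the only definition given for that outcome.
- **Analysis.** "Secondary outcomes will be compared using t-tests for continuous variables and Chi-square tests for dichotomous variables". Each of these yes/no outcomes is therefore tested separately between arms.

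The Randomization process paragraph states that neither women nor midwives can be blinded. No section says how a woman with an episiotomy and no spontaneous tear is to be classified.

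**The concern.** An episiotomy is a wound of the perineum, but it is not a tear. A definition of intact perineum that excludes only tears therefore lets in women whose perineum has been cut. For the same reason, a second-degree outcome worded as a tear leaves them out.

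This matters more here than in many trials. The decision to cut is made after randomization by staff who know the allocation, and the intervention is the presence of a colleague at that very moment. The protocol itself treats episiotomy as something that may differ between arms, because it lists it as an outcome. If use differs, cuts can take the place of tears. The arm with more cuts then looks better on second-degree tears and on intact perineum, although the share of women with perineal trauma is the same. The direction is unknown: lower use with two midwives would hide a real benefit rather than create a false one.

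The aim and the outcome also do not match clearly. If grade II trauma is meant to include episiotomy, the tear-only outcome does not measure the aim. If it is not, replacing a tear by a cut counts towards the aim.

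**Working it through.** **1. Classifying one woman under the stated wording.** Take a woman with an episiotomy and no spontaneous tear.

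| Outcome in Project design | Literal reading |
|---|---|
| Episiotomy | yes |
| First-degree tear | no |
| Second-degree tear | no (no tear) |
| Intact perineum | yes (no tear) |

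She counts as intact and as an episiotomy at once.

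**2. Checking the formula on the protocol's own figure.** Inputs from Project design: 4.1% against 2.0%, 80% power, 5% level taken as two-sided, 1:1 allocation. With the mean proportion p̄ = 0.0305,

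n = [1.960·√(2·0.0305·0.9695) + 0.842·√(0.041·0.959 + 0.020·0.980)]² / 0.021²

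= (0.4766 + 0.2043)² / 0.000441 ≈ 1051.4, rounded up to 1052.

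This matches the stated 1052 per group. The randomized number also follows: 1052 × 1.4 = 1472.8, so 1473.

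**3. Illustrating the size for second-degree tears.** Inputs:
- 78% second-degree tears among primiparous women (Background, from a regional study);
- 1473 per arm as randomized, or 1052 as the required analysed number;
- assumed: one arm has d percentage points more episiotomies, each replacing one second-degree tear, with no other difference between arms.

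The chance of a significant difference is Φ[(d − 1.960·SE₀)/SE₁], where SE₀ = √(2·p̄(1−p̄)/n) and SE₁ = √[(p₁(1−p₁) + p₂(1−p₂))/n].

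Worked case, d = 4 points and n = 1473: p₁ = 0.78, p₂ = 0.74, p̄ = 0.76. SE₀ = 0.01574 and SE₁ = 0.01572. (0.04 − 0.03084)/0.01572 = 0.582, and Φ(0.582) = 0.72.

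| Assumed shift | Tear-only rates | Relative risk | Chance at 1473 per arm | Chance at 1052 per arm |
|---|---|---|---|---|
| 1 point | 78% vs 77% | 0.99 | 9.5% | 7.9% |
| 2 points | 78% vs 76% | 0.97 | 25.1% | 19.2% |
| 3 points | 78% vs 75% | 0.96 | 48.4% | 36.8% |
| 4 points | 78% vs 74% | 0.95 | 72.0% | 57.5% |

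With no shift the chance is the nominal 5%, both directions together. In every row the rate of second-degree tear or episiotomy is equal in the two arms, so the combined outcome shows no difference.

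**4. Does the starting point matter?** The protocol does not say whether the 78% includes episiotomies. Suppose tears plus cuts total 78% and the lower-use arm has an assumed episiotomy rate of 5% (tear-only 73%) or 10% (tear-only 68%). At 1473 per arm, a 3-point shift then gives 43.8% or 40.7%, and a 2-point shift 22.6% or 21.0%. The picture is the same, slightly smaller.

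**5. Intact perineum.** No base rate is given. If cut-only women raise it by 2 points from an assumed 5%, the chance of significance is 63% at 1473 per arm (49% at 1052). From an assumed 10% it is 41% (31%). For 1 point, the figures at 1473 are 22% and 14%. At these base rates the outcome is more sensitive than second-degree tears.

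**The case against.** The strongest reply is that the protocol lists outcomes and contains no scoring rule. Reporting episiotomy as its own outcome does not exclude it from grade II, and the aim's word trauma can include a cut. In ordinary language an incised perineum is not intact, so the bracket may be no more than a short gloss. The coding of overlapping categories is often left to the analysis plan or case report form, and neither is at hand. Episiotomy prevalence is reported by arm, so a shift would be seen. The size depends on an assumed one-for-one substitution, and the documents give no rate and no reason to expect a shift.

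Much of this stands, and it limits the point. A reader might infer four stronger things that the text does not support:

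- **That the protocol instructs sites to score episiotomy outside grade II.** It gives no such instruction. The result follows only from reading the outcome wording literally.
- **That the bracket contradicts the listing of vaginal, labial and periurethral tears.** Those are listed separately, so the bracket most naturally means no perineal tear.
- **That these outcomes could not be interpreted at all.** A shift in episiotomy would be visible, and a combined rate can be computed from data already planned.
- **That every episiotomy should be regraded as at least second degree.** The Background assigns it no grade. This is a classification choice that the review should not impose.

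What the reply does not remove is the bracket itself. It is a stated definition, not silence, and it admits a cut perineum. Separate rates for tears and episiotomy do not show how many women had a cut alone, so a reader of the tables could see a shift but not correct for it.

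**Conclusion.** The point holds for two secondary outcomes, intact perineum and second-degree tears. It is a definition to be repaired and not a flaw in the main comparison: the primary outcome of grade III-IV tears does not change, and the sample size reproduces.

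How far the results could be distorted cannot be known from the protocol, because it gives no episiotomy rate. The calculated range runs from slight (a 1-point shift) to substantial (3 to 4 points). It rests on each extra episiotomy replacing a second-degree tear without extension, on the 78% applying to this population, and on a shift that the documents do not predict in either direction. A smaller shift or partial substitution would reduce it. The repair is nonetheless worth making, because it removes this distortion whatever the shift turns out to be.

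**What to change.** In Project design, where the secondary outcomes are listed:

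1. Define intact perineum as no perineal tear of any grade and no episiotomy.
2. Report second-degree tear or episiotomy as a combined outcome beside second-degree tears alone, and say which of the two answers the grade II aim.
3. Keep the episiotomy rate as its own outcome.

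The cost is a change of wording and one extra reported figure. Episiotomy and the tear types are already planned outcomes, so no new data are needed. The combined figure will differ from tear-only rates published elsewhere, which is why both should be shown.
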